#### **11.5.5 Methods for Categorical and Count Data**

Generalized estimating equations (GEEs) (Diggle, Liang, and Zeger, 1994) will be used to analyze categorical (binary, ordinal, nominal) and count outcome measures. The statistical issues arising from clustering of subjects within a site requires appropriate statistical methods for analysis of clustered binary data just as it is for continuous normal data. The GEE model is appropriate for the Poisson distribution of our primary outcome number of occasions. The GEE methodology allow for the analysis of categorical and count data which may be missing for some subjects either because of a missed week or due to drop-out, thus complete information for all subjects is not needed. The PROC GENMOD in SAS® [SAS Institute Inc. Cary, NC] will be used to carry out these analyses.

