In the analysis, we plan to use statistical models that do not require complete observations on all subjects (MEM, GEE). However, the validity of the inference based on these models still depends on whether or not the assumptions on which these models are based are satisfied in our data. One important assumption in all these models is that the missing data is missing 'at random', i.e. the missing mechanism does not depend on the value of the unobserved outcome. Unfortunately, this assumption is un-testable in most medical research and in our study as well. One approach to this problem is to assume a model for the missingness mechanism that does depend on the unobserved outcome value and to do the analysis (i.e. estimate the treatment effect) incorporating the assumed model for the missingness. There are parametric and semi-parametric methods for doing so (Diggle et al., 1994; Kenward, 1998; Rotnitzky et al. 1998, Scharfstein et al. 1999; Liu et al. 1999). Comparison of the inferences from assuming various models for the missingness provides a measure of the validity of the efficacy estimate from the model that assumes missing 'at random'. Another approach to sensitivity analysis is based on the computation of a local sensitivity index which measures the change in the estimated intervention effect in a neighborhood of the 'missing at random' model for missingness (Rotnitzky et al. 2001; Ma and Heitjan (in press)). We plan to perform a sensitivity analysis based on these two approaches in order to assess the effect of the assumption of missing 'at random' being violated on the inference regarding the treatment efficacy.

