## 11.6 Analysis of specific hypotheses

### 11.6.1 Primary hypothesis

Hypothesis 1: SSB intervention will significantly outperform the HE condition with respect to decreasing the number of penetrative intercourse occasions that are unprotected.

The following marginal model for outcome of count will be used to test this hypothesis:

$$(1) \quad \log E(Y_{ijkt}) = \beta_0 + \beta_1 X_{ijk} + \beta_2 t + \beta_3 X_{ijk} t + \gamma_1 Z_{1ijk} + \gamma_2 Z_{2ijk}$$

where  $Y_{ijkt}$  is the value of the primary outcome measure at time  $t$ ,  $t=0$  for 3 months post intervention and  $t=1$  for 6 months post-intervention, for the  $i^{th}$  subject in the  $j^{th}$  intervention group (cluster) in the  $k^{th}$  CTP site (strata);  $X_{ijk}$  is intervention indicator ( $X_{ijk}=1$  for the experimental intervention and  $X_{ijk}=0$  for the control intervention);  $Z_{1ijk}$  is the value of the outcome measure prior to intervention;  $Z_{2ijk}$  is the monogamy status prior to intervention. The model parameters will be estimated by GEE (generalized estimating equation) approach that makes use of all available data and takes into account the within site, within treatment group, and within subject correlations in the way insensitive to the specification of correlations.

The regression parameters in this model correspond to intervention effects of interest. For example, statistically significant from 0 parameter  $\beta_3$  indicates that over time the effects of the two study interventions are different;  $\beta_3 < 0$  corresponds to the effect of the experimental intervention increasing over time faster than the effect of the experimental intervention;  $\beta_3 = 0$  corresponds to no difference in the effectiveness of the interventions over time. If  $\beta_3 = 0$ , the parameter  $\beta_2$  estimates the rate of change in the outcome measure from 3 to 6 months post-intervention in the two intervention groups, and the parameter  $\beta_1$  estimates the difference between the experimental and control intervention, which is the same at the two follow-up assessment times.

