We clarify that each parameter in the model corresponds to a distinct question. A statistically significant coefficient for the interaction term ( $\beta_3$ ) will indicate that the intervention effect is different at 3 and 6 months; in this case, different intervention effects will be estimated for 3 and 6 months post intervention. If the interaction term is not significant, the intervention effect will be estimated with the coefficient for the main effect of the intervention,  $\beta_1$ . The coefficient for monogamy status will be used to assess the effect of monogamy, etc. We maintain that no multiple testing adjustment is necessary – with the proposed strategy for testing the hypothesis that the experimental intervention will be superior to the control intervention with respect to number of unprotected sex occasions.

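### Missing at random is not enough for the unweighted GEE primary analysis when 6-month dropout depends on the 3-month count, and the choice of working correlation then matters

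*Protocol*

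**What the plan says.** Section 11.5.7 of the protocol introduces the two model families together: "we plan to use statistical models that do not require complete observations on all subjects (MEM, GEE". It then says "One important assumption in all these models is that the missing data is missing 'at random", and defines this as meaning that "the missing mechanism does not depend on the value of the unobserved outcome". Later in the same section the main efficacy estimate is treated as coming from a model that assumes missing at random, and the sensitivity analyses are set up around it.

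Section 11.5.5 presents dropout as no obstacle to GEE, because outcomes may be "missing for some subjects either because of a missed week or due to drop-out, thus complete information for all subjects is not needed". Section 11.6.1 fixes the primary analysis: "The model parameters will be estimated by GEE (generalized estimating equation) approach that makes use of all available data". No weights are mentioned, and the correlations are said to be handled "in the way insensitive to the specification of correlations". If the intervention-by-time coefficient β3 is significant, "in this case, different intervention effects will be estimated for 3 and 6 months post intervention"; otherwise the main effect β1 is reported.

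Section 11.5.7 also puts forward propensity-score multiple imputation as the general approach. It arrives there from the example of a woman with baseline data only. It does not say whether a missing 6-month count is imputed for a woman seen at 3 months, or from which predictors.

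**The concern.** The definition in 11.5.7 allows a woman to miss the 6-month visit because of what she reported at 3 months, since that value is observed. A correctly specified likelihood mixed model remains valid in that case. An unweighted GEE in general does not: its estimating equations are unbiased on available data if missingness depends only on the covariates in the mean model. In model (1) those are arm, time, baseline count and monogamy status. The 3-month count is an outcome there, not a covariate.

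Two things are at stake. First, the bias falls on the 6-month effect while the 3-month effect is untouched, so it feeds into β3, which decides how the result is reported. Second, the planned sensitivity analyses examine departures from missing at random. They do not cover the gap between missing at random and what an unweighted GEE needs, so they would surround a reference analysis that is itself not generally valid under missing at random.

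**Working it through.** **Inputs from the protocol.** Control mean 17, with 15, 15.5 or 16 under SSB; Poisson variance equal to the mean; within-woman correlation ρ1 = 0.4, 0.6 or 0.8; ρ2 and ρ3 for group and site (section 11.2); 480 women; model (1) (section 11.6.1).

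**Assumptions, because the protocol gives none.** Dropout of 10%, 20% or 30% at 6 months; complete 3-month data; the logit of dropout changes by 1 per SD of the 3-month count; and, for over-dispersed counts, an SD of about 24 or a log-scale SD of about 1.1.

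**1. Reproducing the protocol's figure.** Table 1 of section 11.2 gives power 0.85 for 17 v 16 with ρ = 0.40/0.10/0.05 and no over-dispersion. With K = 5 groups of m = 4 per arm at each of 12 sites:

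SE² = (17+16)/12 × [((1+ρ1)/2 + (m−1)ρ2)/m − ρ3]/K = 2.75 × [(0.70+0.30)/4 − 0.05]/5 = 0.11, so SE = 0.332.

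Power = Φ(1/0.332 − 1.96) = Φ(1.055) = 0.854. All 72 entries without over-dispersion in the two tables reproduce within 0.005, so the variance and correlation inputs are read as intended.

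**2. The mechanism.** Take no true effect (17 v 17), dropout tied to the 3-month count in one arm only, independence working correlation and no baseline adjustment. If retained women average d SDs below the full arm at 3 months, their 6-month mean is 17 − ρ1 × d × SD. So

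exp(β3) ≈ 1 − ρ1 × d × SD/17.

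With Poisson variance, SD/17 = 4.123/17 = 0.2425. At 20% dropout and 1 logit per SD, d = 0.18:
- ρ1 = 0.4: 1 − 0.4 × 0.18 × 0.2425 = 0.983
- ρ1 = 0.6: 1 − 0.6 × 0.18 × 0.2425 = 0.974
- ρ1 = 0.8: 1 − 0.8 × 0.18 × 0.2425 = 0.965

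Simulation gives the same three values. Over 10-30% dropout and the three values of ρ1, the simulated range is 0.991 to 0.951. With SD about 24 and correlation about 0.6, simulation gives 0.829 at 20% dropout. That corresponds to d of about 0.20: 1 − 0.6 × 0.20 × 24/17 = 0.83.

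**3. Adding what model (1) contains.** With adjustment for the baseline count and about 20% missing at 6 months, exp(β3), truth 1, is:

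| Dropout dependence | Variance | Independence | Exchangeable within woman |
|---|---|---|---|
| One arm only | Poisson | 0.99-1.01 | 1.00 |
| One arm only | Over-dispersed, log-scale SD about 1.1 | 0.93-1.04 | 0.98-1.01 |

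Values fall below or above 1 according to whether women with higher or lower counts drop out. The over-dispersed runs entered the baseline count on the log scale. Exchangeable correlation by intervention group or site hardly helps: in one unadjusted Poisson run it gave 0.976 and 0.974, against 0.972 for independence. It is the within-woman correlation that matters.

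**4. Same dependence in both arms.** With baseline adjustment the bias is about 1% or less. Without adjustment and with a true 15 v 17 effect (ratio 0.882), the interaction ratio is 1.008 (Poisson) or 1.037 (over-dispersed), and the 6-month ratio is 0.890 or 0.909.

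**5. Effect on the β3 test, and the remedy.** These are rejection rates in 1,000 trials of 480 women with no true effect, 20% dropout, dependence in one arm only and no baseline adjustment (so larger than under model (1)):
- Poisson variance: independence 21.8%, exchangeable within woman 5.2%, inverse-probability weighting 5.1%. With dropout unrelated to the count, independence gives 4.3%.
- Over-dispersed: 26.5%, 9.5% and 7.4%, against 6.6%.

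Weighting used the true retention probabilities and returned interaction ratios of 1.001 (Poisson) and 0.999 (over-dispersed).

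**6. Is over-dispersion likely?** Section 11.2 cites baseline means of 13.7, 17.4 and 20.9 in three arms of an earlier study, a range of 7.2. With independent counts of variance 17, the 5% limit for that range is 3.31 × 4.12/√n, which equals 7.2 at n = (13.64/7.2)² = 3.6 women per arm. Those arm sizes are not given, but a variance near 17 looks too small.

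**The case against.** The strongest reply has five parts.

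- **The text calls missing at random one important assumption, not the only one.** This is correct. A reader might infer that the protocol declares it sufficient for GEE; it does not say so outright. What stands is that no other missing-data condition is named for GEE, and that the section goes on to treat the main estimate as one that assumes missing at random.
- **Multiple imputation is offered as the general approach.** A reader might infer that only women with baseline data alone would be imputed. The text does not settle that: baseline-only women are one example, and the exceptions that follow differ by outcome, not by dropout pattern. Imputation that covered missing 6-month counts and used the 3-month count would largely remove the problem. But the scope is unclear beside the all-available-data wording of 11.6.1. Predictors can be left to an analysis plan.
- **Independence is the worst case.** Section 11.6.1 says the within-subject correlation is taken into account, and section 11.5.4 says the sample size used the analysis model, which includes ρ1. This largely stands, and it is why the bias may be negligible. It also shows that the specification is not immaterial.
- **A false interaction needs dropout dependence that differs by arm.** This stands when there is no true effect, and nothing in the protocol shows such a difference. It is conceivable: five sessions against one (6.1), no participant blinding (6.3.2), and partner anger at condom introduction or negotiation as a foreseeable harm (8.5).
- **Follow-up of all randomised women is planned, by phone if needed (8.0, 8.3).** This may keep dropout low. No rate is stated.

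**Conclusion.** The point holds as one of correctness, with a conditional and mostly modest size. Section 11.5.7 gives GEE a missing-data condition that is too weak for an unweighted fit to available data, and the insensitivity claim in 11.6.1 fails when 6-month dropout depends on the 3-month count.

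Under the protocol's own Poisson variance and model (1), the distortion of the interaction ratio is about 1% even with independence. It reaches about 4-7% only if three conditions meet: strongly over-dispersed counts, dependence that differs by arm, and an independence working correlation. Modelling the within-woman correlation brings it down to about 2% or less. The dropout rate, its dependence on the count and the over-dispersed SD are all assumed.

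A reader might go further and conclude that any dropout related to the 3-month count produces a false interaction, or that the 6-month effect will be materially wrong. The documents do not support either: the first needs a difference between arms or a true effect, and the second needs counts and a working correlation that the protocol does not specify.

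**What to change.** - **Correct section 11.5.7.** State that missing at random suffices for the likelihood mixed models, and that an unweighted GEE generally needs missingness to depend only on covariates in its mean model, or a within-woman correlation that is about right. Remove or qualify the insensitivity claim in 11.6.1.
- **Make the primary estimate valid under missing at random**, in one of two ways. Either state that the multiple imputation covers every missing 3- or 6-month count, not only those of women with baseline data alone, and uses arm, baseline count and 3-month count. Or weight the GEE by the inverse probability of being observed, with those predictors in the weight model.
- **Keep the planned non-random sensitivity analyses** around that reference.

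The cost is wording, one imputation or weighting step, and slightly wider confidence intervals. No new data are needed.

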## 11.6 Analysis of specific hypotheses

### 11.6.1 Primary hypothesis

Hypothesis 1: SSB intervention will significantly outperform the HE condition with respect to decreasing the number of penetrative intercourse occasions that are unprotected.

The following marginal model for outcome of count will be used to test this hypothesis:

$$(1) \quad \log E(Y_{ijkt}) = \beta_0 + \beta_1 X_{ijk} + \beta_2 t + \beta_3 X_{ijk} t + \gamma_1 Z_{1ijk} + \gamma_2 Z_{2ijk}$$

where  $Y_{ijkt}$  is the value of the primary outcome measure at time  $t$ ,  $t=0$  for 3 months post intervention and  $t=1$  for 6 months post-intervention, for the  $i^{th}$  subject in the  $j^{th}$  intervention group (cluster) in the  $k^{th}$  CTP site (strata);  $X_{ijk}$  is intervention indicator ( $X_{ijk}=1$  for the experimental intervention and  $X_{ijk}=0$  for the control intervention);  $Z_{1ijk}$  is the value of the outcome measure prior to intervention;  $Z_{2ijk}$  is the monogamy status prior to intervention. The model parameters will be estimated by GEE (generalized estimating equation) approach that makes use of all available data and takes into account the within site, within treatment group, and within subject correlations in the way insensitive to the specification of correlations.

The regression parameters in this model correspond to intervention effects of interest. For example, statistically significant from 0 parameter  $\beta_3$  indicates that over time the effects of the two study interventions are different;  $\beta_3 < 0$  corresponds to the effect of the experimental intervention increasing over time faster than the effect of the experimental intervention;  $\beta_3 = 0$  corresponds to no difference in the effectiveness of the interventions over time. If  $\beta_3 = 0$ , the parameter  $\beta_2$  estimates the rate of change in the outcome measure from 3 to 6 months post-intervention in the two intervention groups, and the parameter  $\beta_1$  estimates the difference between the experimental and control intervention, which is the same at the two follow-up assessment times.

We clarify that each parameter in the model corresponds to a distinct question. A statistically significant coefficient for the interaction term ( $\beta_3$ ) will indicate that the intervention effect is different at 3 and 6 months; in this case, different intervention effects will be estimated for 3 and 6 months post intervention. If the interaction term is not significant, the intervention effect will be estimated with the coefficient for the main effect of the intervention,  $\beta_1$ . The coefficient for monogamy status will be used to assess the effect of monogamy, etc. We maintain that no multiple testing adjustment is necessary – with the proposed strategy for testing the hypothesis that the experimental intervention will be superior to the control intervention with respect to number of unprotected sex occasions.

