### **6.3.1 Randomization**

The randomization will be within strata (CTP site). According to CTN coding, each site is a separate program or location. Separate block randomization schedules will be

developed for each CTP. This randomization scheme was chosen over individual randomization in order to hold the waiting time to group intervention to 4 weeks post baseline assessment. Under an individual randomization plan, excessive waiting periods might be necessary in order to accumulate enough subjects to conduct an intervention group. It should be noted that this randomization scheme poses the potential problem of imbalance between intervention conditions – in the event that a CTN sample (N = 40) is fulfilled by 5 cohorts of 8 subjects.

In each participating CTP clinic site, we will initially use block randomization to randomly assign our target (N=40) subjects to our intervention conditions in 6 cohorts. After baseline assessment, subjects will be placed into an open cohort awaiting randomization to one of the two intervention conditions. Randomization will be carried out either: when a cohort of 8 women has been recruited; or 4 weeks has passed since the first subject was placed in the cohort, whichever comes first. In the event that 3 participants have not been recruited in four weeks, the window will stay open until at least 3 participants have been recruited. Once closed, the cohort will be randomly assigned to one of the two intervention conditions – either the one receiving SSB intervention or the other receiving HE. If recruitment is rapid, a site may exceed the target of N=40 in 6 cohorts, up to approximately 48 subjects. If recruitment is slow, and <40 subjects have been randomized, we will initiate a second block randomization. If < 29 subjects (or an average of <5 subjects/group) have been recruited, a block randomization schedule for 4 more cohorts will be used. If 29 – 34 subjects have been recruited in the initial 6 cohorts, a block randomization schedule for 2 more cohorts will be used. If 35 – 39 subjects have been recruited in the initial 6 cohorts, 1 additional cohort will be randomly assigned.

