### **11.2 Sample Size and Statistical Power**

The sample size is determined to ensure sufficient power (at least 80%) of a significance test (with level of significance  $\alpha=0.05$ ) to detect a clinically meaningful intervention effect with respect to the primary outcome measure (number of unprotected penetrative sex occasions).

The study design is a stratified cluster randomization trial (Donner and Klar, 2000). The intervention groups constitute the clusters. Each intervention group will consist of approximately 3 to 8 women depending on the number of eligible subjects recruited in the fixed time interval of 4 weeks. The strata are the 12 CTP sites – in which 40 participants per stratum will be enrolled. Thus, within each stratum, 5 to 10 clusters will be randomized in a balanced fashion to the two interventions. Below is presented the power of the test for comparison of the two interventions subject to these design and recruitment restrictions. Tables 1 and 2 were developed for different counts of CTPs (with the number of subjects per CTP fixed at 40). The two tables corresponding to 12 CTPs (and shown in the protocol) resulted in power values that were closest to our goals.

The power analysis for the stratified cluster randomization trial is based on a test statistic proposed by Liu & Liang (1997). The test statistic is based on generalized estimating equation (GEE). The power analysis takes into account the fact that data are correlated (repeated observations on a subject, the measurements of subjects belonging to the same intervention group (cluster) and from the same CTP (strata) and that the outcome follows a non-normal distribution.

The test statistic is actually a quasi-score statistic based on the generalized estimating equation. The asymptotic distributions of the test statistic under  $H_0$  and  $H_1$  are both known. In the analysis we assume the outcome (the number of unprotected sex occasions) follows a Poisson distribution with the marginal mean being a function of the intervention. In this case, under the null hypothesis the test statistic converges to Chi-square distribution with 1 degree of freedom. Under the  $H_1$ , the test statistic converges to non-central Chi-square distribution with 1 degree of freedom. After we specify the parameters in the linear predictor for the mean and in the covariance matrix of the outcome (that is, the working correlation matrix which does not have to be necessarily

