## **11.5 Analytic Plan**

### **11.5.1 Testing and estimation**

All testing will be two-sided and significance will be judged at level  $\alpha=0.05$ . Effects will be reported with point estimate and 95% confidence intervals in addition to p-values.

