The design of our study – to conduct each intervention within each CTP site – makes stratification by CTP a significant source of benefit to power. This benefit strongly offsets the detrimental effect of within CTN correlation. We have made adjustments for the fact that within CTP correlation has a detrimental effect on power – by decreasing the effective degrees of freedom associated with an intervention. For example, our design calls for 20 subjects within each CTP to be assigned to each of the two interventions; the within CTP correlation decreases the 40 degrees of freedom to a number that depends on the size of the correlation. (Please note that the group nature of the intervention is another source of decrease in degrees of effective freedom – due to correlation within group). These conditions have been taken into account in the sample size computations. In fact, the larger the within CTP correlation, the better the power is. Stratification by CTP results in a more powerful test – much like the paired t-

test is more powerful than the two-sample t-test when pairs of observations are known to be associated. (The pairs of observations in this study are the means of the outcome for the experimental and control interventions within CTP site). Sample size computations are performed using the exact model that will be used in the analysis. These computations take into account both the (relatively small) detrimental effect of within CTP correlation and its (relatively large) beneficial effect. The interaction between site and intervention effect is treated as random effect with variance  $\sigma^2$ .

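### Primary model (1) omits the randomisation stratum and names no GEE cluster: the uncorrected Wald test is too liberal with 12 site clusters, and cohort clusters can forfeit the stratification gain counted in the power

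*Protocol*

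**What the plan says.** Section 6.3.1 randomises whole cohorts of women within each site. Section 11.2 calls the design a stratified cluster randomised trial, with the cohorts as clusters and 12 sites as strata, "in which 40 participants per stratum will be enrolled". The end of section 11.2 and section 11.5.4 both explain that a larger site correlation raises power, because the two arms are compared within each site. Section 11.5.4 adds: "Sample size computations are performed using the exact model that will be used in the analysis".

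Model (1) for the primary count has terms for intervention, time, their interaction, the baseline count and monogamy status. It has no site term. Estimation is by GEE, said to be one that "takes into account the within site, within treatment group, and within subject correlations in the way insensitive to the specification of correlations". The cluster level is not named, nor is the form of the test or any small-sample correction. Section 11.5.5, on count outcomes, mentions one level only: "The statistical issues arising from clustering of subjects within a site requires appropriate statistical methods for analysis of clustered binary data". Model (2), for continuous secondary outcomes, does carry random site, site-by-intervention and cohort effects.

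On error rates, section 11.5.1 says "All testing will be two-sided and significance will be judged at level" 0.05.

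**The concern.** Standard GEE with a sandwich variance, as run in PROC GENMOD, has one level of independent clusters. It is robust to misspecified correlation inside that level and assumes independence between clusters. The primary model therefore has two possible readings.

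- **Site is the cluster.** Site, cohort and subject correlation are all covered, and the covariance between arms within a site is captured, so the stratification gain is kept. But there are only 12 clusters, too few for an uncorrected sandwich error with a normal reference.
- **Cohort is the cluster.** Cohorts from one site are treated as independent. With no site term, the standard error ignores the stratification that the power tables count.

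The primary p-value and confidence interval would depend on an unstated programming choice, and the second reading contradicts the statement that power and analysis use the same model.

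**Working it through.** **Inputs (protocol).** Two-sided 0.05. 12 sites of 40 women. Layouts per site: ten cohorts of 4 (five per arm, Table 1), or five cohorts of 8 (three HE, two SSB, Table 2). Means 17 vs 15.5 or 16; Poisson variance. Correlations: ρ1 (same woman) 0.4-0.8, ρ2 (same cohort) 0.10-0.15, ρ3 (same site) 0.05-0.10.

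**1. Reproducing the printed power.** Take the within-site difference of arm means over two follow-ups. With n women per arm per site and cohort size m, each arm contributes

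V = μ[(1+ρ1)/2 + (m−1)ρ2 − mρ3]/n.

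The −mρ3 term is the credit for stratification. SE = √((V_HE + V_SSB)/12) and power = Φ(difference/SE − 1.96). At 0.6/0.1/0.05, 17 vs 16:

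- Ten of 4: bracket 0.80 + 0.30 − 0.20 = 0.90. V = 17×0.90/20 = 0.765 and 16×0.90/20 = 0.720. SE = √(1.485/12) = 0.352. Power 0.81 (printed 0.81).
- Five of 8: bracket 0.80 + 0.70 − 0.40 = 1.10. V = 17×1.10/24 = 0.779 and 16×1.10/16 = 1.100. SE = √(1.879/12) = 0.396. Power 0.715 (printed 0.71).

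For 17 vs 15.5 the same steps give 0.990 and 0.969 (printed 0.99 and 0.97). All cells without over-dispersion in both tables reproduce within half a percentage point. The tables therefore assume a within-site comparison.

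**2. Cohorts as clusters, no site term, no help from baseline.** The reported variance loses the −mρ3 term, while the true variance keeps it.

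- Ten of 4: SE ratio √(1.10/0.90) = 1.106; reported SE 0.389. Power Φ((1 − 1.96×0.389)/0.352) = 0.75. Type I error 2Φ(−1.96×1.106) = 3.0%.
- Five of 8: SE ratio √(1.50/1.10) = 1.168; reported SE 0.462. Power Φ((1 − 1.96×0.462)/0.396) = 0.59. Type I error 2.2%.

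Over all the protocol's correlations and both layouts, the SE ratio is 1.08 to 1.53 and type I error 0.3-3.4%. The largest fall for 17 vs 16 at ρ1 = 0.6 is from 0.89 to 0.62 (five of 8, 0.6/0.1/0.1). For 17 vs 15.5 the lowest power is 0.85. If the baseline count carries the site effect, simulated type I error is 4.2-4.9%, so most of the conservatism goes.

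**3. Sites as clusters, Wald z.** In the balanced case without covariates, the sandwich divides by 12 rather than 11. The test then rejects when |t₁₁| > 1.96×√(11/12) = 1.877, which has probability 8.7%. With 10 df, the limit 1.96×√(10/12) = 1.789 gives 10.4%. Simulations of model (1) (1,500-2,500 trials per scenario), for the single intervention coefficient:

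| Test, site clusters | Protocol variance | Skewed counts (assumed CV 0.5-2.5) |
|---|---|---|
| Wald z | 7.7-9.3% | 9-12% |
| t, 10 df | 5.0-5.7% | 5.9-7.8% |

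The robust score test gave 3.8-5.1%.

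**4. Cohort clusters with site indicators.** With a degrees-of-freedom correction and t reference, type I error is 4.2-5.3% (5.2-6.1% skewed). Without the correction it is 6.6-8.5% (8.4-10.5% skewed). These runs contain no site-by-intervention variance, which section 11.5.4 treats as random. Suppose that variance is an assumed 2-5% of the outcome variance. With ten of 4 under the null (mean 17, 0.6/0.1/0.05), the within-site variance is 2×0.765 = 1.530, and the interaction adds 0.02×17 = 0.34 to 0.05×17 = 0.85. Type I error is 2Φ(−1.96√(1.530/1.870)) = 7.6% to 2Φ(−1.96√(1.530/2.380)) = 11.6%. Site clusters absorb this variance.

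**5. Power with an honest reference.** On t with 11 df at 0.6/0.1/0.05, power for 17 vs 15.5 is 0.974 (ten of 4) and 0.935 (five of 8). For 17 vs 16 it is 0.735 and 0.634.

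**The case against.** **The cluster is implied.** The text on within-site correlation and section 11.5.5 both point to site, and in a marginal model site may enter through the covariance. This stands in part. On that reading the stratification is not lost, and the missing site term alone does not prove a departure from the power model. What remains is the small number of clusters, and the fact that the cluster is never named.

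**The inflation depends on the test.** The only GEE test the protocol names is the quasi-score statistic of section 11.2, and a robust score test holds its level. This is right. But section 11.2 names it for the power calculation; section 11.6.1 speaks of significant coefficients and names no test.

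**This is detail for an analysis plan.** The choice of correction often is. Here, however, the protocol writes out the primary model, claims insensitivity for it and says that the power rests on the same model. Those statements need to agree.

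**Stronger readings that a reader might infer.**

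- *Type I error of 14% or more.* For model (1)'s single coefficient the simulations gave at most about 12%. Testing the interaction first, as section 11.6.1 describes, gives 11.1% under the protocol's variance and 12.5-15.6% with skewed counts, but that adds a separate problem of the testing sequence.
- *The primary result is wrong whichever cluster is used.* Not so: a score test with site clusters, or cohort clusters with an informative baseline, stays close to 5%.
- *The untransformed baseline count gains almost nothing.* Under the protocol's variance it cuts the variance of the estimate by 21-32%, the same as log(baseline + 1). It fails only with heavy skew (CV about 1.5 or more), and the protocol gives no empirical SD.

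**Conclusion.** The point holds in this form. Model (1) leaves out the stratum that the design and the power calculation rely on, and its claim to handle all three correlations holds only with 12 site clusters. With those, an uncorrected Wald z-test runs at about 8-9% under the protocol's variance, and 9-12% under assumed skew. With cohort clusters and no site term the error is one of lost power, not false positives. It is material for 17 vs 16 and modest for 17 vs 15.5, and it applies to the extent that baseline does not absorb the site effect. The power figures rest on the protocol's Poisson variance and its ranges of correlation. The target, "The sample size is determined to ensure sufficient power (at least 80%) of a significance test", is still met for 17 vs 15.5 at 0.6/0.1/0.05 after the correction.

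**What to change.** In section 11.6.1, add site to model (1), name the GEE cluster, and pre-specify a test that is valid for few clusters. There are two acceptable routes.

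1. Site as cluster, with a t reference on about 10-11 df or a robust score test. This also absorbs the random site-by-intervention variance of section 11.5.4. The simulated levels for this route come from model (1) as written, without site indicators.
2. Cohort as cluster, with site indicators, a bias-corrected sandwich error and a t reference, stating that this assumes no site-by-intervention variance.

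Correct the section 11.5.4 statement that power and analysis use the same model, and let section 11.5.5 acknowledge clustering by cohort as well as by site. Log(baseline + 1) is only an optional safeguard if counts prove heavily skewed.

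The cost is wording, code and some degrees of freedom. No data collection changes. Stated power falls slightly: on 11 df, 17 vs 15.5 is about 0.97 (ten of 4) and 0.94 (five of 8), against 0.99 and 0.97 printed.
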